The results of this study may help synthesize complex intraoperative clinical information and unveil novel therapeutic strategies. Derived from data from the QEII Hospitals, the results would be directly applicable to the care of Nova Scotians. The models may lead to the creation of objective risk stratification scores calculated at the end of surgery, to identify high risk patients for increased postoperative follow-up and monitoring. Moreover, if models created using machine learning perform well, machine learning may be used more frequently to reveal the patterns within complex, large perioperative datasets. Hemodynamics are potentially modifiable risk factors. Future research includes prospective studies on whether targeted hemodynamic goals, increased postoperative follow-up of high-risk patients, and real-time machine learning precision medicine could improve outcomes after surgeries.

Specific aims

1. To use machine learning techniques to investigate systematically intraoperative hemodynamic predictors of postoperative 30-day all-cause mortality (primary outcome) and major in-hospital morbidity. Hemodynamic predictors to be studied are blood pressure, heart rate, oxygen saturation, end-tidal carbon dioxide, and medications to adjust blood pressure. Please see “Outcomes” section below for full list of secondary outcomes.
2. To evaluate performance of machine learning models created and compare the performance of the best model to the Surgical Apgar Score.

Hypothesis

Controlling for other predictors, the durations of mean arterial pressure (MAP) <65mmHg, heart rate <60 or >100 beats per minute (BPM), hemodynamic medications use, oxygen saturation (SpO₂) <88%, and end-tidal carbon dioxide (EtCO₂) <30 or >45 will be associated with postoperative 30-day all-cause mortality (primary hypothesis) and 30-day major in-hospital morbidity (secondary hypothesis). Note that blood pressure, heart rate, vasopressors and

inotropic medications, oxygen saturation, and end-tidal are considered key indicators of hemodynamics. We have chosen conventional ranges commonly used in practice, and will perform sensitivity analysis of different definitions of each hemodynamic variable.

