We will exclude patients with no intraoperative anesthetic records. Cardiac surgery patients (identified by procedure anatomy “Heart” or “Cardiac” within Innovian) are excluded since they have a unique set of considerations and complications due to having surgery directly in the heart. To include the full spectrum of non-cardiac surgical patients, no specific surgeries will be excluded except for deceased organ donation (“organ retrieval” in Innovian procedure name, and American Society of Anesthesiologists classification for neurologically-deceased organ donors, ASA=VI).

Preliminary analysis of our intraoperative database estimates approximately 35,000 patients in this cohort. For patients with multiple procedures, the date of the first surgical procedure with an overnight stay will be used to identify the specific surgical admission of interest.

Data Sources

The de-identified dataset will consist of databases from Innovian, Horizon Surgical Manager (HSM), and Health Data Nova Scotia (HDNS). Innovian is the intraoperative anesthesia electronic information management system used at the QEII, containing automated recordings of intraoperative standard monitors, time-stamped anesthesiology entries of medications and interventions, and perioperative laboratory tests. HSM contains vital signs and administrative data at the anesthetic preoperative clinic, in the preoperative area prior to the surgery, and in the recovery room after surgery.

The specific HDNS databases to which access is being requested are the Canadian Institute for Health Information (CIHI) Discharge Abstract Database (DAD) and Vital Statistics. DAD is a repository of clinical and administrative data from each hospitalization, including preoperative diagnoses, surgery performed, postoperative complications, and investigations.

DAD includes the 25 most relevant diagnoses preoperatively and postoperatively. Nova Scotia physician billings data will not provide any additional relevant information and are not necessary for this project. The Vital Statistics database records all deaths within Nova Scotia. Innovian and HSM data will be linked together by health card number and surgical date by the Innovian Data Manager (Innovian-HSM dataset). The health card numbers will be sent to Medavie for encryption. HDNS will link the Innovian-HSM dataset with the HDNS variables by encrypted study IDs and surgery date. National and provincial privacy and data security policies will be strictly followed.

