Intraoperative	
 • Anesthetic factors 
 ○ Type of anesthesia: General vs. regional vs. neuraxial vs. sedation (multiple concurrent types possible) ○ Measures of anesthetic depth 
 ▪ Age-adjusted inspired Minimal Alveolar Concentration (MAC) – summed from all volatile anesthetics used (36). Since MAC is available for every 15 seconds, the average MAC for each case (i.e. time-weighted) will be used.

	
 ▪ Bi-spectral Index (BIS): duration in minutes for BIS <46 (37) 
 ○ Temperature: duration (minutes) a) < 36°C, and b) > 38°C (38) ○ Crystalloid administration >1L: volume in mL • Surgical factors 
 ○ Duration ○ Laparoscopy ○ Bleeding: Estimated blood loss (mL), lowest Hemoglobin day within 2 days after surgery (g/L) (including day of surgery), Red Blood Cell transfusion (mL)
--	---

Analysis plan

Statistics will be analyzed directly on the HDNS Citadel secure server using SAS Software 9.4 (SAS Institute, Inc., NC) and R version 3.5.3 (<https://www.r-project.org/>).

Cohort characteristics

Descriptive statistics will be performed on all proposed predictors and outcome variables listed above. Continuous variables will be listed as mean with standard deviation, and categorical variables as frequency counts and percentages. Mortality will also be described in terms of causes, location (in- vs. out-of-hospital), and timing (intraoperative vs. postoperative, and by postoperative day).

Data processing and artifact removal

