 2. Heart rate > 170 or < 30 BPM will be removed. To reduce the influence from outlier artifacts (e.g. temporary disconnection or adjustment of a monitor), single episodes of deviation in any variable greater than 50% above or below the preceding value will be flagged. If the flagged heart rate from the pulse oximeter and ECG (and/or arterial line) differ by >10 , the heart rate will be removed as artifact.
2. Clarification about “Baseline” heart rate: similar to BP above, the HSM and first Innovian HR will be modeled separately during analysis, i.e. each patient will have two “baseline” HR. All patients will have the variable of a first Innovian HR (after artifact clean up). Only some patients will have HSM HR (i.e. preoperative clinic or in the preadmission area). If a patient does not have a HSM HR, the variable value will be coded as missing (not zero).

- **EtCO₂** will only be analyzed in cases involving general anesthesia. Values > 120 or < 5 mmHg will be removed as artifact.
- **SpO₂** > 100% or < 50% will be removed as artifact.
- **Temperature** < 30 or > 43 degrees Celsius will be removed as artifact.
- **End tidal volatile concentrations** (including nitrous oxide) will be converted to summed age-adjusted MAC (36). The total age-adjusted MAC < 0.2 and > 2.5, at each 15 second interval, will be removed as artifact prior to calculation of the time-weighted average (15 second time intervals).

For each automatically recorded variable from Innovian, at least 3 cases will be reviewed to ensure correct artifact labeling. We will quantify the percentages of artifacts flagged and removed per case for each variable monitored.

Artifact Removal Sub-study: Derivation of a machine learning algorithm for artifact removal for invasive blood pressure data

Rationale

While putting together the Innovian dataset for our study, we found that existing artifact (noise) removal algorithm has limitations at removing invasive arterial blood pressure (IABP) artifacts. Current algorithms are based on clinician-generated rules (40). We plan to use machine learning algorithms to improve artifact detection.

Objective

Our goal is to derive an artifact removal algorithm for IABP using machine learning of hemodynamic data.

Methodology

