Since intraoperative hemodynamics are automatically recorded and mortality reporting is mandatory, we do not expect significant missing data for the key hemodynamic predictors and primary outcomes. For disease conditions, patients without ICD codes are assumed to not have the disease; the same applies for medications. For the other variables of interest, if there is less than 5% missing data, no processing will be performed. Between 5-20%, missing data will be imputed using group mean (43) for continuous variables. At greater than 20% missing data, the variable will be removed from analysis with potential causes evaluated and reported.

Creating the models

We will divide the cohort temporally (approximately 80:20 ratio) into two groups: derivation/training group (approx. January 1, 2013 – Dec 31, 2016), and validation group (approx. Jan 1, 2017 – December 1, 2017). This temporal approach to the model building vs. validation groups will also mirror the real-life application of machine learning, where data from the past is used to predict future outcomes. Splines will be used for the hemodynamic predictors involving time as a unit.

In the derivation/training set, we will create models for the *primary outcome* using machine learning techniques, including logistic regression with variable selection, classification trees, and Principal Component Analysis (PCA)(21). We have chosen these techniques to obtain interpretable results, i.e. being able to understand the process by which the algorithm decision making occurred. Also, these techniques demonstrate different approaches and perspectives to better understand the relationships amongst the variables.

Logistic regression with variable selection (e.g. LASSO, Elastic Net) identifies the most important predictors to create a parsimonious model. Classification trees predict outcomes based on input variables through classification. Random forest is an ensemble method of classification trees; while it is not directly interpretable, it can show which predictor has the highest importance. Association rule learning will be used to find new patterns. PCA is used for

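### EtCO2 belongs to the primary hypothesis but is analysed only under general anesthesia, and the plan does not say how patients without general anesthesia enter the adjusted mortality models

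*Combined protocol and SAP*

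**What the plan says.** - **Hypothesis.** After adjustment for other predictors, the plan expects that durations of several hemodynamic abnormalities, including "end-tidal carbon dioxide (EtCO₂) <30 or >45 will be associated with postoperative 30-day all-cause mortality (primary hypothesis", are related to death. Table 1 lists EtCO2 durations among the main exposures for model building.
- **Study Population.** Apart from cardiac surgery, "no specific surgeries will be excluded except for deceased organ donation". Nothing is excluded by type of anesthetic.
- **Table 2, intraoperative predictors.** Type of anesthesia is a candidate covariate: "General vs. regional vs. neuraxial vs. sedation (multiple concurrent types possible". The text above the table keeps only the covariates that are statistically significant.
- **Data processing and artifact removal.** EtCO2 "will only be analyzed in cases involving general anesthesia".
- **Missing data.** The section opens with "we do not expect significant missing data for the key hemodynamic predictors and primary outcomes". It then sets three bands for the remaining variables: below 5% nothing is done, from 5% to 20% a group mean is filled in for continuous variables, and "At greater than 20% missing data, the variable will be removed from analysis".
- **Sensitivity and subgroup analysis.** Type of anesthesia is one of the planned subgroups.

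**The concern.** Read together, these sections leave one of the hypothesised exposures undefined for every patient who had no general anesthesia. The absence comes from the plan's own rule, not from a recording failure, so automatic recording does not prevent it.

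Three matters are left open:
- which patients the adjusted EtCO2 association is estimated in;
- what value patients without general anesthesia carry when EtCO2 sits in the same model as blood pressure, heart rate, oxygen saturation and vasoactive drugs;
- whether the associations for those other exposures are estimated with or without these patients.

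The exposure durations are derived from Innovian before linkage, so the coding may be settled by default before the analysts see it. Elsewhere the plan does deal with this kind of absence. A patient with no HSM blood pressure or heart rate is to be coded as missing and not as zero, and emergency and elective cases are separated for changes from baseline pressure. EtCO2 has no equivalent instruction.

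**Working it through.** **1. The plan's own figure.** Inputs from Power calculation: 24,000 derivation patients, 1.7% mortality, at least 10 events per predictor.

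Events = 24,000 × 0.017 = 408. Predictors = 408 / 10 = 40.8, which the plan gives as 41. Both figures reproduce.

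**2. Patients affected.** The documents do not give the share q with no general-anesthesia component, so q is an assumption here. Mortality is taken as equal in both groups.

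Patients affected = 24,000 × q. Deaths affected = 24,000 × q × 0.017. Events left if these patients are dropped = 408 × (1 − q).

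| q (assumed) | Patients affected | Deaths affected | Events left | Events left / 10 |
|---|---|---|---|---|
| 10% | 2,400 | 41 | 367 | 36.7 |
| 20% | 4,800 | 82 | 326 | 32.6 |
| 30% | 7,200 | 122 | 286 | 28.6 |
| 40% | 9,600 | 163 | 245 | 24.5 |

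If mortality without general anesthesia were twice that with it (overall still 1.7%), the events left would be 272 at q = 20% and 220 at q = 30%.

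**3. What the missing-data text does with EtCO2.** The bands are written for variables other than the key hemodynamic predictors, and the Hypothesis section counts EtCO2 among the key indicators. Read literally, EtCO2 has no rule, and a standard logistic fit drops every row without a value.

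If the bands were nevertheless applied, the result would depend only on q:
- below 5% (fewer than 1,200 of 24,000): no processing, so these rows still drop out of a regression that contains EtCO2;
- 5% to 20% (1,200 to 4,800): these patients receive a mean EtCO2 duration that was never analysed for them;
- above 20% (more than 4,800): EtCO2 is removed and that part of the primary hypothesis goes untested.

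**4. Whether filling in a value is harmless.** This was checked by an illustrative simulation with assumed inputs: 100 replicates of 24,000 patients, and a true log odds ratio of 0.10 per 10 minutes among general-anesthesia cases. The table gives the mean estimate at q = 30%. The rows vary the odds of death without general anesthesia relative to general-anesthesia cases with no abnormal EtCO2 time.

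| Relative odds | Mean fill, no indicator | Zero fill, no indicator | Either fill with indicator | General anesthesia only |
|---|---|---|---|---|
| 2 | 0.085 | 0.042 | 0.098 | 0.098 |
| 1 | 0.098 | 0.095 | 0.095 | 0.095 |
| 0.5 | 0.112 | 0.129 | 0.099 | 0.099 |

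With the indicator in the model, the filled value does not matter and the estimate equals the one from general-anesthesia cases alone. Without it, the estimate moves in either direction once baseline risk differs between the groups. At q = 4% the effect is small: with relative odds of 2, zero fill without the indicator gives 0.090 against 0.098.

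**The case against.** Restricting EtCO2 to general anesthesia is reasonable, and any good repair keeps that restriction. The gap can fairly be called an omission in the text. The anesthesia-type subgroup would yield a within-general-anesthesia estimate. Appendix 1 lists anesthesia type as a covariate, and zero minutes with that covariate in the model would come close to the repair proposed here. All of this stands, and it limits how serious the point is. It does not close the gap: the subgroup analysis does not say how EtCO2 enters the main models, and the text above Table 2 makes retention of anesthesia type depend on significance.

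A reader might also infer four stronger things that the documents do not support:
- **That the plan will impute EtCO2 up to 20% and delete it above.** The bands, as worded, are for other variables, and below 5% nothing is done. Which outcome would follow is unknown because the share is not stated.
- **That there is one mortality model and every technique loses these patients.** Several techniques are planned, and trees may treat absent values differently from regression.
- **That the comparison with the Surgical Apgar Score must rest on different patients.** All models are to be evaluated in the validation set, and nothing prevents scoring both on the same people.
- **That bispectral index and temperature durations share the problem.** A patient without a temperature probe still has a temperature, so the value is unmeasured and not inapplicable. Both variables are listed among the other predictors, which the bands do cover.

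**Conclusion.** The point holds and should be fixed before analysis. The plan names EtCO2 in its primary hypothesis, keeps patients for whom it rules EtCO2 out, and expects no appreciable missing data in that class of predictor. These statements cannot all stand. A regression run as written either drops patients without general anesthesia or uses a filled value without a guaranteed general-anesthesia term.

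The size depends on the unstated share. At 10% to 40% of the derivation set it is about 2,400 to 9,600 patients and 41 to 163 deaths, assuming 24,000 patients and equal mortality of 1.7%. Cases that combine general with another technique count as general, which lowers the share. The simulation shows that the coding can matter and in which directions; it does not predict the bias in this cohort.

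**What to change.** State the following in the analysis plan:
- All patients stay in the main models.
- A general-anesthesia indicator is forced in, exempt from significance-based selection and from the LASSO or elastic-net penalty. Appendix 1 describes anesthetic type as mandatory in Innovian, so the indicator should be available for essentially everyone.
- The EtCO2 terms, including any spline terms, are nested within that indicator, with a constant such as 0 for patients without general anesthesia. Trees and random forest use a not-applicable level.
- EtCO2 is reported as an association within general anesthesia, and the other exposures are reported for the full cohort.
- Not-applicable EtCO2 is exempt from the 5% and 20% thresholds. EtCO2 that is truly missing within general anesthesia gets its own stated rule.
- The share of patients without general anesthesia, and their deaths, are reported.

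An acceptable alternative is a prespecified model in general-anesthesia cases only for the EtCO2 hypothesis, with the other exposures estimated in the full cohort.

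The cost is SAP wording, one derived indicator and one to three extra model terms, set against the plan's limit of 41 predictors. No new data are needed.

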For this sub-study, we will include patients with IABP recorded. There are approximately 6000 patients with IABP recordings. We will exclude patients who do not have any recording of the required hemodynamic variables: IABP systolic, IABP mean, IABP diastolic, non-invasive blood pressure (NIBP) systolic, NIBP mean, NIBP diastolic, IABP heart rate, ECG heart rate, SpO₂ heart rate, and SpO₂ (oxygen saturation).

To label the dataset with “gold-standard” answers, we will use a random sample of 60 cases (chosen by random number generator) for which the artifacts (anomalies) will be manually labeled by anesthesiologists on the study team, blinded to the final artifact removal algorithm.

The problem of artifact detection (anomaly detection) will be addressed for two target variables: IABP mean and IABP systolic. We will use the same methodology to conduct the analysis for artifacts detection in these two target variables.

For each target variable the problem will be tackled in two approaches: as a univariate time series and as a multivariate time series. In the univariate series approach, we will only take into consideration the data of the time series representing either the IABP mean or the IABP systolic artifacts. For the multivariate approach, we will include the information of the following variables IABP systolic, IABP mean, IABP diastolic, NIBP systolic, NIBP mean, NIBP diastolic, IABP heart rate, ECG heart rate, SpO2 heart rate, and SpO2 (oxygen saturation).

In the univariate case, the anomaly detection will be carried out using several statistical approaches, and machine learning approaches.

Methods to apply for anomaly detection in the univariate time series case:

- 1) Statistical-based approaches: ARIMA model, simple, double and triple Exponential Smoothing and Outlier Detection using Prediction Confidence Interval (PCI). Anomalies will be detected by evaluating the deviation of the predicted point to the observed one.
- 2) ML-based approaches: DBSCAN, LOF, isolation Forest, One-Class Support Vector Machine, XGBoost and neural networks.

Regarding the anomaly detection in the multivariate time series case we will apply several machine learning-based techniques such as isolation forest, One-Class Support Vector Machine, XGBoost and different neural networks.

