Regarding the performance evaluation, we will split the data set into train/test (70%) and validation (30%). This means we will use 42 cases for train and test and 18 cases for validation. The performance evaluation in the train/test part of the data will be carried out using 100 repetitions of bootstrapping method and we will assess the performance on following metrics: F1, precision, recall, specificity, Negative Predicted Value (NPV), False Discovery Rate (FDR), G-Mean, AUC-ROC, AUC-PR.

The derived algorithm will be applied to the full sample (~6000 excluding the 60 cases used above), and the percentage of hypotension defined will be quantified according to published comparisons (1). This will also be compared to the results of the MPOG algorithm.

Analysis will be performed in Python.

Research Ethics Considerations

This sub-study will use the existing Innovian dataset, but using only the following completely de-identified variables:

1. Study ID
2. Time stamps for each hemodynamic variable (dates will be removed, and placeholders will be used to denote surgery times that happened overnight that bridges two dates)
3. Required timestamped hemodynamic variables for modelling:
IABP systolic

IABP mean
IABP diastolic
NIBP systolic
NIBP mean
NIBP diastolic
IABP heart rate
ECG heart rate
SpO2 heart rate
SpO2 (oxygen saturation)

Data analysis will be performed by [name] (member of the current study team as a post-doc, currently faculty member at University of Ottawa) and her Co-op student [name] will receive the de-identified, limited Innovian dataset securely and directly from our Innovian manager using the NSHA encrypted institutional email (SENDNS). The files will be stored in a password-protected computer and permanently deleted according to NSHA policy once analysis is complete (estimated to be end of September 2020).

Missing data

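### The artifact sub-study does not provide for scoring the existing rule-based algorithms against the anesthesiologist labels, so it cannot support a claim of improvement over them

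*Combined protocol and SAP*

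**What the plan says.** All of this is in the combined protocol and SAP, section Artifact Removal Sub-study, unless stated otherwise.

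- **Rationale.** Existing algorithms are described as limited for invasive arterial blood pressure (IABP) and as built on rules written by clinicians. The response is: "We plan to use machine learning algorithms to improve artifact detection".
- **Objective.** The formal aim is narrower: "Our goal is to derive an artifact removal algorithm for IABP using machine learning of hemodynamic data". No superiority hypothesis, margin or test is given.
- **Methodology, labels.** Sixty randomly chosen cases form the reference standard, "for which the artifacts (anomalies) will be manually labeled by anesthesiologists on the study team, blinded to the final artifact removal algorithm".
- **Methodology, methods.** For the univariate series, "the anomaly detection will be carried out using several statistical approaches, and machine learning approaches": ARIMA, exponential smoothing, a prediction-interval method, and a list of machine-learning methods. The multivariate approach lists machine-learning methods only. No rule-based algorithm appears in either list.
- **Methodology, metrics.** The 60 cases are split into 42 and 18. F1, precision, recall, specificity, NPV, FDR, G-mean and two AUCs are specified for the 42-case part, with 100 bootstrap repetitions. The metrics for the 18 validation cases are not spelled out.
- **Methodology, application.** The derived algorithm is then run on the remaining IABP cases, leaving out the 60. There, "the percentage of hypotension defined will be quantified according to published comparisons (1"). The next sentence is "This will also be compared to the results of the MPOG algorithm".
- **Data processing and artifact removal, Blood pressure, Step 1.** The main study cleans blood pressure with MPOG plus two further published rule sets, applied together. The sub-study names only MPOG as a comparator.

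**The concern.** To say that one detector improves on another, both must be measured against the same truth. The sub-study builds that truth for 60 cases, but places its only comparison with an existing algorithm in the cases that lack it.

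A hypotension percentage in unlabelled data is an output of cleaning and does not measure its accuracy. A lower percentage fits removal of falsely low readings, and it fits deletion of real hypotension equally well. A higher percentage is just as ambiguous.

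What is at stake is the conclusion that the sub-study's rationale points towards. A new algorithm could have worse recall or precision than the rules it is meant to replace, and nothing in the planned output would reveal it. The combined rule set, which is what the main study actually uses, has no stated comparison of any kind.

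**Working it through.** **1. The plan's own figures.** 60 × 0.70 = 42 and 60 × 0.30 = 18, so the stated split reproduces. The application sample is about 6,000 − 60 = 5,940 cases. The sub-study states no alpha, power or effect size to reproduce.

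**2. Which methods meet which data.**

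| Method | 60 labelled cases | About 5,940 unlabelled cases |
|---|---|---|
| Time-series and machine-learning candidates | Accuracy metrics planned | Derived algorithm: hypotension percentage |
| MPOG alone | Nothing stated | Hypotension percentage |
| Combined rule set of the main study | Nothing stated | Nothing stated |

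The derived algorithm and the existing rules meet only in the right-hand column, where there is no reference standard.

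**3. Why a rate without labels does not rank accuracy.** As a simple stand-in for the hypotension percentage, take the share of readings flagged. With artifact prevalence p, sensitivity Se and specificity Sp:

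- flagged share f = p·Se + (1 − p)(1 − Sp)
- for fixed f, Sp = 1 − (f − p·Se)/(1 − p)
- F1 = 2·p·Se/(f + p)

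Inputs: p = 0.15 is the maximum for invasive pressure quoted under Data processing and artifact removal, where it is called a likely overestimate. p = 0.05 is an assumption. p = 0.029 is the document's figure for noninvasive pressure, used here only as a low value. The reference accuracy of Se 0.90 and Sp 0.95 is assumed.

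At p = 0.15: f = 0.15 × 0.90 + 0.85 × 0.05 = 0.1775. For Se 0.60, Sp = 1 − (0.1775 − 0.09)/0.85 = 0.897 and F1 = 0.18/0.3275 = 0.550. The other rows follow in the same way.

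| p | f | Se 0.90: Sp, F1 | Se 0.60: Sp, F1 | Se 0.30: Sp, F1 |
|---|---|---|---|---|
| 0.15 | 17.75% | 0.950, 0.824 | 0.897, 0.550 | 0.844, 0.275 |
| 0.05 | 9.25% | 0.950, 0.632 | 0.934, 0.421 | 0.918, 0.211 |
| 0.029 | 7.47% | 0.950, 0.504 | 0.941, 0.336 | 0.932, 0.168 |

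Within each row, three detectors whose F1 differs threefold flag the same share. Equal rates therefore do not imply equal accuracy. Unequal rates do not say which detector is better either, since f rises both with more true detections and with more false ones.

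**4. What a labelled comparison could deliver.** Readings cluster within cases, so precision is governed mainly by the 18 held-out cases. For a paired difference in a metric, the 95% half-width is 1.96 × SD/√18, with the between-case SD assumed:

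- SD 0.1: 1.96 × 0.1/4.243 = 0.046
- SD 0.2: 0.092
- SD 0.3: 0.139

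A t quantile on 17 degrees of freedom (2.11) would widen these by 2.11/1.96 = 1.08.

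**The case against.** **The objective is derivation, not superiority.** This stands. The title and the Objective speak of deriving an algorithm, and the labelled metrics serve that. A reader might infer that the sub-study cannot answer its own question. The documents do not support that: improvement is the motive in the Rationale, and no superiority hypothesis is stated. The gap concerns a claim of improvement only.

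**The plan is silent rather than negative.** This stands in part. The plan does not rule out scoring MPOG on the labels, and the word that opens the MPOG sentence is loose. Its natural antecedent, however, is the hypotension percentage in the sample that leaves out the labelled cases. If the sponsor intends more, one sentence settles it.

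**There is already a benchmark outside machine learning.** True: the time-series methods can be compared with machine learning on the labels. They are not the clinician-written rules that the Rationale finds wanting. The separate review of at least three cases per recorded variable is a quality check without metrics.

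**The main study is affected.** A reader might infer this because hypotension duration is a main exposure. Nothing in the documents feeds the derived algorithm into the main study. Its cleaning is specified as the three rule sets, applied in SQL before the exposure variables are created. The protocol also cites evidence that the choice of artifact algorithm did not significantly alter the association between hypotension and outcome.

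**Eighteen cases may be inconclusive.** Fair. A large count of labelled readings does not answer it, because case length is not given, the 15% rate is a ceiling, and readings are clustered. An interval of modest width is still more than the present plan offers on accuracy relative to the rules.

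**Conclusion.** The point holds in a limited form. As written, the plan yields an accuracy estimate for the new algorithm but no stated accuracy estimate for MPOG or for the combined rules. Its only comparison with existing rules rests on about 5,940 cases without labels, so it cannot support a statement that machine learning detects artifacts better than those rules. The mortality analysis is untouched.

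The conclusion rests on reading the MPOG sentence as referring to the hypotension percentage. It does not depend on the assumed accuracies: the threefold spread in F1 at one flagged share is an illustration, repeated at artifact rates from 2.9% to 15%. The interval widths do depend on the assumed SDs. A fair labelled comparison also assumes that the labellers did not work from the rules' flags; the plan states blinding to the final algorithm only.

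**What to change.** Add to the performance evaluation paragraph of the sub-study's Methodology:

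> The derived algorithm, MPOG alone, and the combined rule set used in the main study (MPOG plus the two further published rule sets in the Blood pressure artifact step) will each be scored against the anesthesiologist labels on the same 18 held-out cases, separately for IABP mean and IABP systolic, using F1, precision, recall, specificity, NPV, FDR and G-mean. Differences between the derived algorithm and each rule-based comparator will be reported with confidence intervals obtained by resampling whole cases. The percentage of hypotension in the unlabelled cases describes the impact of each algorithm and is not evidence of accuracy.

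The AUC metrics are left out for the rules because these give a yes/no flag. The wording also states which metrics apply to the 18 validation cases, which the plan leaves open.

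**Cost.** No new labelling is needed. The sub-study dataset already holds time-stamped IABP systolic, mean and diastolic values, and MPOG results are already planned. The main study's rules run in SQL and the sub-study in Python with a separate analyst, so the rules must be recoded or their flags exported for the labelled cases. That is a small task, but not a free one. The other price is candour about precision: with 18 cases the 95% half-width is about 0.05 to 0.14 under the assumed SDs, and the comparison may be inconclusive.
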